### 3.1.9 Surgeon Effect

363  
364  
365  
366  
367 Random surgeon effects will be tested using a generalized linear model via the SAS  
368 GLIMMIX procedure. This marginal model produces a robust standard error (RSE)  
369 by use of a sandwich estimator, which corrects for correlated data.  
370  
371  
372  
373  
374  
375  
376

### 3.1.10 Analysis of Potential Interaction

377 Potential effect modifiers of donor tissue preservation time such as recipient age or  
378 corneal diagnosis will be screened by including first-order interaction terms.  
379 Variables that exhibit modification of the donor tissue preservation time effect with  
380 an associated P value  $< 0.10$  will be added to the model, and the final model will be  
381 constructed consisting of terms with a p value  $< 0.01$  following a backwards selection  
382 process.  
383  
384  
385  
386

## 3.2 Secondary Analyses of 3 Year Graft Failure

### 3.2.1 Preservation Time

387 The time from preservation to surgery is treated as a binary variable in the primary  
388 analysis (see above section). Secondary analyses will look at the time from  
389 preservation to surgery as a categorical variable with multiple levels and as a  
390 continuous variable:

- 391 • Kaplan-Meier estimates of graft failure with 95% confidence interval will be  
392 calculated for each of the following groups: 0 – 4, 5 – 7, 8 – 11, and 12 – 14 days  
393 from preservation to surgery (counting partial days as whole days).
- 394 • A Cox proportional hazards model will be constructed treating the time from  
395 preservation to surgery as a continuous variable (using time of day to calculate  
396 hours from preservation to surgery). Polynomial terms will be added to assess any  
397 curvilinear, J, or U shaped relationship between time from preservation to surgery  
398 and graft failure. If no significant departure from a linear relation is detected, a  
399 one sided 95% confidence interval will be computed for the hazard ratio per day  
400 of time from preservation to surgery.
  - 401 ▪ The proportional hazards assumptions will be tested through the use of time-  
402 dependent variables with a logarithm transformation of time. If this  
403 assumption is violated then hazard ratios will be presented separately for  
404 different periods following transplant.

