489 **2.5 Subject Enrollment**

490 A maximum of 1330 participants will be enrolled, depending on the number of participants who  
491 enroll both eyes into the study to reach the recruitment goal of 1330 study eyes with a goal to  
492 enroll an appropriate representation of minorities. As the enrollment goal approaches, sites will  
493 be notified of the end date for recruitment. Study participants who have signed an informed  
494 consent form can be randomized up until the end date.

495

496 After the informed consent form is signed, enrollment will be accomplished using the study  
497 website. Enrollment must be completed at least 10 days prior to the date of surgery. The study  
498 participant is then managed according to the investigator's usual routine without regard to the  
499 fact that the study participant is participating in the trial.

500 **2.6 Randomization**

501

502 Randomization of participant eyes will occur via an automated computer program. The  
503 randomization schedule will be stratified by surgeon using a permuted blocks design. The  
504 randomization groups are as follows:

505     • Preservation Time Group:  $\leq 7$  days  
506     • Preservation Time Group: 8-14 days

507

508

509 A study participant may have both eyes enrolled in the study. The eye scheduled for surgery  
510 which will occur first will be assigned randomly to a preservation time group, and the eye  
511 scheduled for surgery which will occur second will be assigned to the alternate group.

512

513

# Chapter 3

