### 3.1.2 Assignment of Donor to Study Eyes

545 The primary eye bank, as designated by the clinical site, will receive a notification when there is  
546 a pending donor assignment. The Eye Bank Procedures Manual provides details regarding the  
547 assignment process. When the eye bank submits an assignment request, a computer program  
548 will use a minimization algorithm to evaluate all available donors and ensure a balance of  
549 subgroups (0-4 days, 5-7 days, 8-11 days, 12-14 days from preservation to surgery) within the  
550 primary randomization groups. Time from preservation to scheduled surgery date will be  
551 calculated as whole days for the purpose of assignment into the appropriate randomized  
552 preservation time group. As surgeons will be masked to all donor information, the label and  
553 report that accompanies the donor will be generated from the study website in such a way to  
554 maintain masking.

556 After the donor assignment procedure is completed, the eye bank will complete a donor  
557 information form on the study website, which includes information about the retrieval of the  
558 cornea (date/time of death, date/time of retrieval, aspects of the processing), cause of death, age  
559 of the donor, and ECD.

560

561 For those assignments where pre-cut tissue has been requested, the eye bank will cut and prepare  
562 the tissue on the same day that they would cut tissue if the donor was being assigned to a non-  
563 study participant for that particular surgeon, and will complete a cutting information form.

564

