### 565 **3.1.2.1 Donor Not Available**

566 If an eligible donor in the correct preservation time window is not available at the primary eye  
567 bank on the date of assignment, attempts will be made by the primary eye bank to import tissue  
568 from another EBAA accredited eye bank. If tissue in the correct preservation time window is  
569 still not available, it will be up to the surgeon to either (1) reschedule the surgery or (2) inform  
570 the participant that they will receive a donor that is otherwise healthy but does not meet criteria  
571 to be in the study and that they will be discontinued from the study.

572

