971 the change in the preservation time effect when the potential confounder is controlled for in  
972 the Cox model. Variables that do not contribute significantly ( $P > 0.05$ ) will be removed  
973 from the model.

974 • Random surgeon effects will be tested using a generalized linear model via the SAS  
975 GLIMMIX procedure. This marginal model produces a robust standard error (RSE) by use  
976 of a sandwich estimator, which corrects for correlated data.

977 • Potential effect modifiers of donor tissue preservation time such as recipient age or corneal  
978 diagnosis will be screened by including first-order interaction terms. Variables that exhibit  
979 modification of the donor tissue preservation time effect with an associated  $P$  value  $< 0.05$   
980 will be retained in the model.

981  
982  
983 **7.2.2 Secondary Analyses of Graft Failure**

984 **7.2.2.1 Preservation Time**

985 The time from preservation to surgery is treated as a binary variable in the primary analysis (see  
986 above section). Secondary analyses will look at the time from preservation to surgery as a  
987 categorical variable with multiple levels and as a continuous variable:

988 • Kaplan-Meier estimates of graft failure with 95% confidence interval will be calculated for  
989 each of the following donor groups: 0 – 4, 5 – 7, 8 – 11, and 12 – 14 days from preservation  
990 to surgery(counting partial days as whole days).

991

992 • A Cox proportional hazards model will be constructed treating the time from preservation to  
993 surgery as a continuous variable (using time of day to calculate hours from preservation to  
994 surgery). Polynomial terms will be added to assess any curvilinear, J, or U shaped  
995 relationship between time from preservation to surgery and graft failure. If no significant  
996 departure from a linear relation is detected, a one sided 95% confidence interval will be  
997 computed for the hazard ratio per day of time from preservation to surgery.

998

999 • The proportional hazards assumptions will be tested through the use of time-dependent  
1000 variables with a logarithm transformation of time. If this assumption is violated then hazard  
1001 ratios will be presented separately for different periods following transplant.

1002

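### Storage-day band within each arm is not randomised, and the four-band and continuous-time graft-failure analyses carry no surgeon or eye-bank term, so within-arm contrasts and the curvature check may reflect site mix

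*Combined protocol and SAP*

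**What the plan says.** **What is randomised.** Protocol 2.6 defines two groups, ≤7 days and 8-14 days. The "randomization schedule will be stratified by surgeon using a permuted blocks design".

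**How the band is chosen within an arm.** Under protocol 3.1.2 a computer program "will use a minimization algorithm to evaluate all available donors and ensure a balance of" the four bands. The balance sought is of "subgroups (0-4 days, 5-7 days, 8-11 days, 12-14 days from preservation to surgery) within the" two randomised groups. Nothing is said about balance within surgeon or eye bank, or about a random element within an arm. Each clinical site designates its own primary eye bank. Protocol 3.1.2.1 provides for import when no eligible donor in the arm's window is available there. The lack of a particular band inside that window triggers nothing.

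**How storage time is analysed for graft failure.** SAP 3.2.1 gives Kaplan-Meier estimates for 0-4, 5-7, 8-11 and 12-14 days. It continues: "A Cox proportional hazards model will be constructed treating the time from" preservation to surgery as a continuous variable, with polynomial terms to look for curved, J or U shapes. A one-sided 95% interval for the hazard ratio per day follows only if no significant departure from linearity is found. Protocol 7.2.2.1 reads the same way. Neither names a surgeon, eye-bank or other covariate term.

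**Where surgeon and eye bank do appear.** A random surgeon effect on graft failure is tested in SAP 3.1.9, under the primary analysis, and is not carried into 3.2.1. Eye bank is not a named factor in SAP 3.1.8 or 3.2.2. Storage medium, who cut the tissue and cut-to-surgery time are listed there, in models that use the binary time group. For endothelial cell density (ECD), SAP 4.2.1 repeats the analyses of 4.1.4, which include an exploratory surgeon random effect but no eye-bank term.

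**The concern.** Randomisation stratified by surgeon makes the two arms comparable in site mix. It does not do so for the bands inside an arm. If some sites supply or receive more of one band, and failure risk differs between sites, a crude comparison of bands mixes the storage effect with the site effect. Overall balance of the four bands does not prevent this.

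Differences in risk between sites are plausible. Surgical technique is tracked but not standardised (protocol 4.1), post-operative care is at the surgeon's discretion (4.2), and banks may use any FDA-approved medium (3.1). The sponsor already thinks a surgeon effect worth testing.

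Two outputs are exposed. The first is the pair of within-arm contrasts, of which 8-11 vs 12-14 days bears directly on use up to the 14-day limit that motivates the trial (protocol 1.2). The second is the check for curvature. A two-arm randomisation identifies only one contrast, so any bend in the curve is learned from within-arm variation. That check also decides whether the per-day interval is computed.

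**Working it through.** **The plan's own figure.** The documents give no precision or power figure for these analyses, only for the two-arm test. With 6% failure in both arms, a margin of 4 points, one-sided 5% and 90% power:

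n per arm = (1.645 + 1.282)² × 2 × 0.06 × 0.94 / 0.04² ≈ 604, total **1208**, as stated. Nothing below changes it.

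**Step 1: how much of the storage-day information is randomised.** Take band midpoints of 2, 6, 9.5 and 13 days and equal band sizes (an assumption).
- Arm means: 4 and 11.25. Between-arm variance = ((11.25 − 4)/2)² = 13.14.
- Within-arm variance = mean of ((6 − 2)/2)² = 4.00 and ((13 − 9.5)/2)² = 3.06, which is 3.53.
- Share between arms = 13.14 / 16.67 = **79%**. If days are spread uniformly within each band, the within-arm variance is 4.68 and the share is **74%**.

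So about 21-26% of the information on a linear slope is non-randomised. For the two within-arm contrasts, all of it is.

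**Step 2: illustration with no true storage effect.** The documents give neither failure rates nor band mix by site, so these are assumptions: half the eyes at sites with 4% failure, half at sites with 8%, overall 6%. Stratification by surgeon puts about 50% of each site type in each arm. If the 4% sites have 15% of their eyes in 0-4 days and 35% in 12-14 days, they must then have 35% in 5-7 and 15% in 8-11. The 8% sites are the reverse.

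| Band | Crude risk |
|---|---|
| 0-4 | (0.15×4 + 0.35×8)/0.50 = 6.8% |
| 5-7 | (0.35×4 + 0.15×8)/0.50 = 5.2% |
| 8-11 | 6.8% |
| 12-14 | 5.2% |

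The within-arm gap is 1.6 points and the difference between arms is zero. A log-linear fit to all four bands gives a hazard ratio of **0.985 per day**. With a 30/20 split the gap is 0.8 points and the hazard ratio 0.993.

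**Step 3: compare with sampling error.**
- Events: 0.06 × 1208 ≈ 72. SE of the log hazard ratio per day ≈ 1/√(72 × 16.67) = 0.029. Since ln 0.985 = −0.015, the bias is about half a standard error.
- Per band: 1208/4 = 302 eyes. The 95% half-width of a within-arm difference = 1.96 × √(2 × 0.06 × 0.94/302) = **3.8 points**, so 1.6 points lies well inside it.

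**Step 4: range.** With a share of 0.5 ± q for the longer band within each arm, site rates from 5%/7% to 3%/9% and q from 0.1 to 0.5, the spurious band gap runs from 0.4 to 6.0 points. The hazard ratio runs from 1.004 to 1.059 per day (or its inverse, if the better sites hold the longer bands). For 4%/8% sites, a gap of 4.0 points needs q = 0.5, meaning that site fixes the band completely. With q = 0 there is no bias. The arm difference is zero throughout.

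**Step 5: curvature.** Keep the 4%/8% sites, but let the 4% sites hold the outer bands (35/15 in one arm, 15/35 in the other). Crude risks become 5.2, 6.8, 6.8 and 5.2%: a false inverted U with no arm difference. The log ratio of middle to outer bands is ln(6.8/5.2) = 0.268. With 604 eyes in each pair of bands its SE is √(1/31.4 + 1/41.1) = 0.237, so the artefact is about 1.1 standard errors. The same site mix thus distorts the curvature check about twice as much, relative to its error, as it distorts the slope.

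**The case against.** A reader might go further and infer that eye-bank supply decides the band and that the dose-response result is therefore confounded by site. The documents do not support that. A program selects the tissue and is designed to balance the bands, and import is available, so supply limits the choice without being stated to determine it. Confounding needs both an unequal band mix and unequal failure risk across sites, and neither is given. Details of assignment are in the Eye Bank Procedures Manual, which is not part of these documents and might add balance by surgeon or bank.

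A reader might also take only the two end bands in the illustration and compute (5.2/6.8)^(1/10) = 0.974 per day. That leaves out the middle bands, which surgeon stratification forces the other way. The four-band fit gives 0.985.

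It can further be said that these are secondary analyses with no decision rule, that no study objective asks where between 8 and 14 days a limit lies, that the covariate lists are open-ended, and that the ECD repeat already carries a surgeon model. All of this stands and limits the weight of the point. It does not remove the gap. SAP 3.2.1 as written adjusts for nothing, not even the factor by which the trial stratifies its randomisation, and the within-arm contrasts have no randomised protection.

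**Conclusion.** The point holds as a possible bias in a secondary analysis that the plan leaves unaddressed. The contrasts 0-4 vs 5-7 and 8-11 vs 12-14 days, and the check for curvature, rest on non-randomised allocation and may carry site confounding. The linear slope is largely protected (74-79% of storage-day variance lies between arms, assuming equal band sizes). The primary non-inferiority test is untouched.

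Under the assumed 4%/8% sites and 35/15 split, the artefact is 1.6 points between bands and about 0.985 per day. That could shift an estimate but would seldom produce a significant result alone. An artefact above 3.8 points would need extreme separation of bands by site or a wide spread of site risk. Actual confounding is neither shown nor excluded by the documents, because band mix and failure rates by site are not given. The reason to act is that the remedy is cheap.

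**What to change.** In SAP 3.2.1:
- Fit the continuous-time Cox model, and a Cox model for 5-7, 8-11 and 12-14 vs 0-4 days, stratified by surgeon or with a surgeon frailty. Report these hazard ratios beside the crude Kaplan-Meier curves, and run the polynomial check in the same model.
- Add a sensitivity analysis by the eye bank that supplied the tissue. The site's primary bank would misclassify imported corneas. Do the same for the ECD repeat in SAP 4.2.1, where only the eye-bank part is missing.
- Tabulate band by surgeon and by eye bank, so that readers can see whether the mix differs.
- Label comparisons within an arm as non-randomised.

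The cost is SAP wording and a model option, with no new visits or measurements and no change to 1208 or 1330. The intervals will be somewhat wider, because strata with no failures add no information. By how much cannot be said, since the documents do not give the number of surgeons or banks. With about 72 expected events, eye-bank strata combined with a surgeon frailty and polynomial terms could be unstable, so eye bank belongs in the sensitivity analysis and not in the main model.

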### 3.2.2 Predictive Factors – (*Analysis plan for objective 3, graft failure outcome*)

405 The association of factors potentially related to graft failure will be evaluated in  
406 univariate and multivariate Cox models, adjusting for preservation time group  
407 regardless of statistical significance. The proportional hazards assumptions will be  
408 tested as described above. Univariate models will be evaluated first, and factors from  
409 those models with a p value  $< 0.10$  will then be evaluated in a multivariate model. A  
410 final model will be constructed consisting of factors with a p value  $< 0.01$  following a  
411 backwards selection process.

412 Potential factors to evaluate include:

- 413 • Recipient factors
  - 414 ➤ preoperative diagnosis

411                   ➤ gender  
412                   ➤ age  
413                   ➤ race  
414                   ➤ prior use of glaucoma medication  
415                   ➤ prior glaucoma surgery (trabeculectomy, laser procedure)  
416                   ➤ current smoker (at time of surgery)  
417                   ➤ lens status (phakic, posterior chamber intraocular lens)  
418                   ➤ Intraocular pressure (IOP)  
419

420                   • Donor/graft factors  
421                   ➤ eye bank determined screening ECD  
422                   ➤ pre-operative CIARC determined ECD  
423                   ➤ age  
424                   ➤ gender  
425                   ➤ race  
426                   ➤ history of diabetes  
427                   ➤ cause of death  
428                   ➤ type of storage medium  
429                   ➤ death to preservation time  
430                   ➤ surgeon cut vs eye bank cut  
431                   ➤ postcut thickness  
432                   ➤ cut to surgery time  
433                   ➤ observations during or after cutting  
434

435                   • Surgical factors  
436                   ➤ Insertion method  
437                   ➤ Incision location  
438                   ➤ Incision site  
439                   ➤ Graft size  
440

441                   • Postoperative factors  
442                   ➤ Dislocation  
443                   ➤ Rebubbling  
444                   ➤ IOP  
445                   ➤ Graft rejection  
446                   ➤ Corneal thickness  
447  
448

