### **4.1 Endothelial keratoplasty procedure**

Surgery (DSEK, DSAEK) will be performed according to the investigator's usual routine. Aspects of the surgical technique and procedure will be tracked, but not standardized. Data to be collected will include incision size, insertion method, air usage, other procedures (e.g. cataract surgery), and operative complications (e.g., difficult donor preparation, difficult placement). *As a reminder, the DMAEK and DMEK procedures will not be acceptable endothelial keratoplasty procedures for the CPTS nor will be PKP.*

608  
609  
610  
611  
612

The surgeon will be masked to donor parameters (e.g. donor age, donor ECD), except the FDA-approved 4°C preservation medium being employed (Optisol GS, Life 4°C, etc.) and parameters needed to perform the surgery (e.g. post-cut thickness). Most importantly the surgeon and study participant will be masked to preservation time.

613  
614  
615  
616  
617

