#### 501 4.1.4 Analysis

502 An ANOVA model with 3 year ECD as the dependent variable will be used to assess  
503 the effect of preservation time.

- 504 505 • Confounding with regard to screening ECD is not expected to be an issue due to  
506 anticipated balance via randomization. Therefore, an ANCOVA model adjusting  
507 for eye-bank-determined screening ECD will only be used if this measurement is  
508 considered good enough to expect to have any impact on reducing variance.
  - 509 510 ○ Although all screening images are being collected, CIARC is not grading  
511 them other than a general quality assessment. CIARC will grade a sample  
512 of screening images within each eye bank. If more than 75% of the graded

509 ECDs are within 10% of the eye bank determined ECDs, the eye bank  
510 determined ECDs will be included in the model.

511 • The time from preservation to surgery will be treated as a binary variable.  
512 • If residual values from the models above are highly skewed then a transformation  
513 (e.g., square root or logarithm) or non-parametric methods will be used instead.  
514 • Random effects will be modeled to account for any correlated data from the same  
515 donor and any correlated data from 2 study eyes of the same study participant.  
516 • Additional ANCOVA models will also adjust for other recipient/donor risk  
517 factors. Univariate models will be evaluated first, and factors from those models  
518 with a p value <0.10 will then be evaluated in a multivariate model. A final model  
519 will be constructed consisting of factors with a p value <0.01 following a  
520 backwards selection process  
521 • Random surgeon effects will also be explored using a mixed effects model.  
522 • Sensitivity analysis will also be performed to check whether results change  
523 meaningfully depending on how missing data are handled. The missing 3 year  
524 ECD values for subjects with surviving grafts at 3 years will be imputed and  
525 included in an analysis as described in the previous section. The data imputation  
526 will be performed by using Rubin's method of multiple imputation.

527

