### 548 4.2.3 Predictive factors – (*Analysis plan for objective 3, ECD outcome*)

549 This analysis also will be limited to subjects with a surviving graft at 3 years. The  
550 association of factors potentially related to 3 year ECD will be evaluated in  
551 univariate and multivariate ANCOVA models, adjusting for preservation time group  
552 regardless of statistical significance, and the reading center grading of pre-operative  
553 ECD (imaged post-cut if the eye bank was performing the cutting and imaged just  
554 prior to shipping if the surgeon was performing the cutting). This ECD value will be  
555 considered the baseline for these analyses. Univariate models will be evaluated  
first, and factors from those models with a p value <0.10 will then be evaluated in a

556 multivariate model. A final model will be constructed consisting of factors with a p  
557 value <0.01 following a backwards selection process.

558 Potential factors to evaluate include:

- 559 560 • Recipient factors
  - 561 ➤ preoperative diagnosis
  - 562 ➤ gender
  - 563 ➤ age
  - 564 ➤ race
  - 565 ➤ prior use of glaucoma medication
  - 566 ➤ prior glaucoma surgery (trabeculectomy, laser procedure)
  - 567 ➤ current smoker (at time of surgery)
  - 568 ➤ lens status (phakic, posterior chamber intraocular lens)
  - 569 ➤ Intraocular pressure (IOP)
- 570 571 • Donor/graft factors
  - 572 ➤ eye bank determined screening ECD
  - 573 ➤ pre-operative CIARC determined ECD
  - 574 ➤ age
  - 575 ➤ gender
  - 576 ➤ race
  - 577 ➤ history of diabetes
  - 578 ➤ cause of death
  - 579 ➤ type of storage medium
  - 580 ➤ death to preservation time
  - 581 ➤ surgeon cut vs eye bank cut
  - 582 ➤ postcut thickness
  - 583 ➤ cut to surgery time
  - 584 ➤ observations during or after cutting
- 585 586 • Surgical factors
  - 587 ➤ Insertion method
  - 588 ➤ Incision location
  - 589 ➤ Incision site
  - 590 ➤ Graft size
- 591 592 • Postoperative factors
  - 593 ➤ Dislocation
  - 594 ➤ Rebubbling
  - 595 ➤ IOP
  - 596 ➤ Graft rejection
  - 597 ➤ Corneal thickness

601 **4.3 Effect of Preservation Time on Pre-Operative ECD – (Secondary Non-Protocol  
602 Objective)**

603 An ANCOVA model with CIARC graded pre-operative ECD as the dependent variable,  
604 and adjusting for eye-bank-determined screening ECD, will be used to assess the effect

605 of preservation time. The time from preservation to surgery will be treated as a binary  
606 variable.  
607  
608

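### The objective 3 predictor models in SAP 3.2.2 and 4.2.3 test operative factors without a surgeon term, so differences between surgeons can be selected as surgical factors

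*Combined protocol and SAP*

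**What the plan says.** SAP 3.2.2 is the analysis plan for the graft-failure part of objective 3, which covers donor, operative and postoperative factors. It specifies "univariate and multivariate Cox models, adjusting for preservation time group". Factors with univariate p<0.10 go forward, and the "final model will be constructed consisting of factors with a p value" below 0.01 after backward selection. Four surgical factors are listed, beginning with "Insertion method", followed by incision location, incision site and graft size. The donor/graft list adds "surgeon cut vs eye bank cut". No surgeon term, frailty, stratum or clustered variance is named.

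SAP 4.2.3 applies the same candidates and selection rule to 3-year ECD, adjusting for preservation group and reading-centre pre-operative ECD, again without surgeon. Protocol 7.2.2.2 also describes a Cox model with no surgeon term.

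On technique, protocol 4.1 says that surgery "will be performed according to the investigator's usual routine" and that "Aspects of the surgical technique and procedure will be tracked, but not standardized". Protocol 3.1.2 has the eye bank cut tissue on the day it would have done so for a non-study patient of the same surgeon.

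Surgeon does appear elsewhere. SAP 3.1.9 tests random surgeon effects within the primary graft-failure analysis. SAP 4.1.4 says of 3-year ECD: "Random surgeon effects will also be explored using a mixed effects model". Protocol 2.6 stratifies randomisation by surgeon. SAP 3.2.2 and 4.2.3 refer to none of these.

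**The concern.** Preservation time is randomised within surgeon, so surgeon differences are largely balanced across that contrast. Operative factors have no such protection. If a surgeon inserts most grafts the same way, that surgeon's eyes are not independent evidence about insertion method, because they share the surgeon's skill, postoperative habits and patients. A Cox model that treats eyes as independent then understates the standard error for that factor, and its hazard ratio mixes technique with surgeon.

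At stake is the operative part of objective 3. A factor that survives to p<0.01 would be read as a technique that affects graft failure or cell density, when it might only separate one set of surgeons from another.

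**Working it through.** **1. The plan's own figure.** SAP 2.0 assumes 6% failure in both groups, a 4-point margin, one-sided 5% error and 90% power.

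n per group = (1.645 + 1.282)² × 2 × 0.06 × 0.94 / 0.04² ≈ 604, total 1208, as stated. Allowing for 10% incomplete follow-up gives 1208 × 1.10 ≈ 1329 or 1208 / 0.90 ≈ 1343; the plan uses 1330. Expected failures are 1330 × 0.06 = 79.8, or 1208 × 0.06 = 72.5. About 80 events at most therefore inform every predictor.

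**2. Simulation inputs.** From the SAP: 1,330 eyes, 6% failure at 3 years, 10% dropout, cut-offs 0.10 and 0.01. Assumed, because the documents do not give them:
- 30, 50 or 70 surgeons with uneven caseloads;
- SD of the surgeon log-hazard of 0, 0.3, 0.5 or 0.8. The last three correspond to 3-year risks between the 16th and 84th percentile surgeon of 4.3–7.7%, 3.3–8.6% and 2.0–9.5%;
- a binary factor with no true effect, the habit of half the surgeons.

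Each setting had 3,000 replicates, so the Monte Carlo standard error near 1% is √(0.01 × 0.99 / 3000) ≈ 0.2 points.

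**3. Factor fixed by surgeon, eyes treated as independent** (Cox score test). Percentage of trials passing p<0.10 / p<0.01:

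| Surgeon SD | 30 surgeons | 50 surgeons | 70 surgeons |
|---|---|---|---|
| 0 | 10.8 / 1.1 | 9.4 / 0.6 | 10.1 / 0.8 |
| 0.3 | 14.8 / 2.9 | 13.4 / 2.2 | 11.7 / 1.0 |
| 0.5 | 22.0 / 5.8 | 19.3 / 3.5 | 16.4 / 3.0 |
| 0.8 | 37.9 / 16.3 | 30.7 / 10.8 | 26.1 / 7.2 |

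With no surgeon variation the test is close to nominal, so the excess comes from clustering.

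**4. Several factors.** With 50 surgeons and SD 0.5, four independent null factors give 1 − (1 − 0.0347)⁴ ≈ 13% chance of at least one false surgical factor, against 1 − 0.99⁴ = 3.9% nominal.

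**5. Factor only partly set by surgeon** (50 surgeons). Percentage passing p<0.01, by share of eyes departing from the surgeon's habit:

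| Surgeon SD | 0% | 10% | 25% | 50% (unrelated to surgeon) |
|---|---|---|---|---|
| 0.3 | 2.2 | 1.5 | 1.1 | 0.7 |
| 0.5 | 3.5 | 3.3 | 1.5 | 1.0 |
| 0.8 | 10.8 | 6.7 | 3.3 | 0.9 |

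**6. After the change.** With a surgeon-clustered variance and a t reference on (surgeons − 2) degrees of freedom, the p<0.01 rate is 0.2–0.6% and the p<0.10 rate 8.5–9.9% in every setting, so somewhat conservative at 0.01. A separate simulation with gamma frailty (variance 0.1–0.5, 40–70 surgeons, log rate-ratio test) gave 1.3–8.7% uncorrected and 1.1–1.8% with clustered errors. The direction agrees; the exact calibration depends on the test used.

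**7. Limits.** Both simulations test one factor at a time, without the full backward selection. Neither covers ECD, where the argument is the same but unquantified.

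**The case against.** A reader might infer that technique is constant within each surgeon. The documents do not say so: a usual routine can include choices made eye by eye, and pre-cut tissue is requested per assignment. Step 5 shows that this matters, because inflation shrinks quickly as technique varies within surgeon. The number and heterogeneity of surgeons are also unknown, and with 70 fairly similar surgeons (SD 0.3) there is no inflation at p<0.01. It would therefore be too strong to say that the standard errors are too small; they are too small to the extent that both conditions hold.

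Nor are the final models adjusted for preservation group alone. Diagnosis, age, race, glaucoma history, lens status and IOP are candidates, so recorded case mix can enter. Unrecorded surgeon differences cannot. Nor are 3.2.2 and 4.2.3 the only models with a surgeon-linked factor: SAP 3.1.8 screens cut-to-surgery time, though as a confounder of preservation time.

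SAP 3.1.9 may show little surgeon variation, in which case the problem is small. But nothing in the plan carries that result into 3.2.2, and little detected variation is not proof of none.

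The strongest objection concerns the remedy. A clustered variance corrects the p-value but leaves the hazard ratio mixing technique with surgeon. Stratifying by surgeon separates them only where technique varies within surgeon, and at a price. With 80 failures and 10% departure from habit, information is about 80 × 0.09 = 7.2 (SE 0.37), against 80 × 0.25 = 20 (SE 0.22) unstratified for a balanced factor. Reaching p<0.01 would need an observed hazard ratio near exp(2.576 × 0.373) ≈ 2.6. This stands, so the stratified estimate belongs in a supplementary role.

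**Conclusion.** The point holds in conditional form. SAP 3.2.2 and 4.2.3 test factors that protocol 4.1 leaves to the surgeon, with no allowance for surgeon, and so the p<0.10 / p<0.01 rule can admit between-surgeon differences. Under the assumptions listed above, the false-positive rate at p<0.01 for a factor fixed by surgeon runs from about nominal to about 16 times nominal. The size in this trial cannot be settled from the documents.

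It would be wrong to read this as a threat to the main result. The non-inferiority comparison is randomised within surgeon and does not use these models, and the sample size is unaffected. The issue concerns secondary association analyses and is worth correcting because the correction is cheap.

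**What to change.** In SAP 3.2.2, base every p-value and confidence interval in the univariate screen and the backward selection on a surgeon-clustered sandwich variance or a shared surgeon frailty. In SAP 4.2.3, include a random surgeon effect in the same steps.

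As a supplementary analysis, for operative factors that vary within surgeons, report an estimate stratified by surgeon and accept its lower precision. Tabulate each operative factor by surgeon. Report any factor that hardly varies within surgeon as an association that cannot be separated from surgeon.

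The cost is SAP wording and minor programming. Surgeon is already recorded as the randomisation stratum, and the SAP already names sandwich and mixed-model methods. The downside is wider intervals for operative factors and fewer of them retained.
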